5 SAMPLE SIZE

Sample size determination is not based on statistical power calculation.

1) Neoadjuvant Cohort:

The SCCHN tumor types will contain 21 HPV-positive and 21 HPV-negative evaluable subjects. MCC and HPV positive cervical, vaginal, or vulvar cancers tumor types will contain 21 evaluable subjects each. A sample size of 21 can detect, with more than 66% and 89% probability, a safety event that occurs at an incident rate of 5% and 10%, respectively. Assuming 10%, 15%, and 20% for pathologic complete response rate, a sample size of 21 can detect, more than 89%, 97% and 99% probability, at least one pathologic complete response respectively.

1) Recurrent/Metastatic Monotherapy Cohort:

HPV+ SCCHN, GYN, MCC and NPC tumor type in the recurrent/metastatic cohort will contain 23 subjects. Table 5-1 shows the probabilities of observing 0, 1 or 2 responders and \square 3 responders assuming 5%, 20% and 30% true response rate of ORR. shows the two sided 95% exact CI using Clopper-Pearson methods based on observed 3, 4 and 5 responders out of 23 subjects.

EBV+ Gastric tumor type will contain approximately 12 subjects, due to the low prevalence. Table 5-3 shows the precision of the estimation of ORR based on the two-sided 95% exact CI using Clopper Pearson methods based on 1, 2, 3, 4 and 5 responders out of 12 subjects. Assuming the

true ORR is 25%, 12 subjects can provide approximately 84% probability to observe at least 2 responders.

Table 5-1: Probability of observing responses given true ORR for sample size of 23 subjects

True ORR	Probability of observing 0,1 or 2 responses	Probability of observing ≥ 3 responses
5%	89.5%	10.5%
20%	13.3%	86.7%
30%	1.6%	98.4%

Table 5-2: Two-sided 95% exact CI using Clopper-Pearson method based on number of observed responses out of 23 subjects

The number of observed responses	3	4	5
Observed Response Rate	3/23 (13.0%)	4/23 (17.4%)	5/23 (21.7%)
95% exact CI	(2.8%, 33.6%)	(5.0%, 38.8%)	(7.5%, 43.7%)

Table 5-3: Two-sided 95% exact CI using Clopper-Pearson method based on the number of observed responses out of 12 subjects

Number of observed responses	1	2	3	4	5
Observed Response Rate	1/12 (8.3%)	2/12 (16.7%)	3/12 (25.0%)	4/12 (33.3%)	5/12 (41.7%)
95% exact CI (%)	(0.2, 38.5)	(2.1, 48.4)	(5.5, 57.2)	(9.9, 65.1)	(15.2, 72.3)

2) Recurrent/Metastatic Combination Cohort:

The HPV+SCCHN, MCC, and NPC tumor types in the recurrent/metastatic cohort will each contain approximately 40 subjects that will be enrolled to the Combo A treatment arm. Patients with cervical cancer and other HPV associated tumors (vulvar/vaginal/anal canal/penile) tumor type will be randomized in a 1:1 ratio to one of two dosing schema (Combo A or Combo B). Approximately 40 subjects will be randomized into each dosing schema. With Revised Protocol 06, no new subjects will be randomized in the anogenital HPV associated tumors cohorts.

Additionally, the metastatic cervical Combination B cohort will be expanded to treat approximately 50 subjects as first-line treatment for their recurrent/metastatic disease if unfit or unsuitable to receive platinum-based therapy and approximately 20 subjects as second-line treatment for their recurrent/metastatic SCC of the cervix to confirm the efficacy signal. With

Combo B and the Combo B expansion, there should be a total of approximately 75 subjects with first-line treatment and approximately 35 subjects with second-line treatment of cervical cancer (approximately 110 cervical subjects total).

The HPV+ SCCHN with prior PD-1/PD-L1 treatment tumor type will be enrolled in Metastatic Combination Cohort (Combo C). Combo C will contain approximately 40 subjects. However, at Revised Protocol 05, no new subjects will be enrolled in this cohort.

Approximately 40 HPV negative and HPV indeterminate I-O naive SCCHN subjects will be enrolled to the Combo D treatment arm. With Revised Protocol 06, no new subjects will be enrolled in this cohort.

Sample sizes of each treatment arm in each tumor type are summarized in Table 5-4.

Table 5-4: Sample size in recurrent/metastatic combination cohort

	Combo A Nivo-3mg/kg q2w + Ipi-1mg/kg q6w	Combo B Nivo-1mg/kg + Ipi- 3mg/kg q3w x 4 followed by Niov 240mg q2w	Combo C Nivo+ BMS- 986016	Combo D Nivo+Dara
Cervical	40	110 ^a		
Anogenital HPV associated tumors (vaginal/vulvar/anal canal/penile)	40	40		
MCC	40			
NPC	40			
HPV+ SCCHN (I/O naive)	40			
HPV+ SCCHN (Prior PD-1/PD-L1)			40	
I-O Naive SCCHN				40

^a Includes 40 from Combination B and 70 from Combination B expansion.

In this study, an ORR in excess of 10% will be considered of clinical interest. Assuming the true ORR is 25%, 40 subjects in each tumor type can provide approximately 79.8% power to reject the null hypothesis that the true ORR is \leq 10%, considering a two-sided alpha of 5%. In addition, Table 5-5 shows the precision of the estimation of ORR based on the two-sided 95% exact CI using Clopper Pearson methods based on 8, 9, 12, 16 and 20 responders out of 40 subjects. At observed more than or equal to 9 responders, i.e., $ORR \geq 22.5\%$, the lower bound of the 95% CI excludes 10%.

Table 5-6 shows the precision of the estimation of ORR based on the two-sided 95% exact CI using Clopper-Pearson methods based on 20, 22, 26, 30, 33, and 35 responders out of 50 subjects.

At observed more than or equal to 22 responders, i.e., $ORR \geq 44\%$, the lower bound of the 95% CI excludes 30%; at observed more than or equal to 26 responders, i.e., $ORR \geq 52\%$, the lower bound of the 95% CI excludes 37%.

Table 5-7 shows the precision of the estimation of ORR based on the two-sided 95% exact CI using Clopper-Pearson methods based on 3, 5, 8, 10, 12 and 14 responders out of 35 subjects. At observed more than or equal to 8 responders, i.e., $ORR \geq 22.9\%$, the lower bound of the 95% CI excludes 10%.

Due to the low prevalence of EBV+ Gastric tumor types and the current investigation of this tumor type in other BMS-sponsored studies, combination cohorts in this study will no longer include EBV+ Gastric tumor type.

Table 5-5: Two-sided 95% exact CI using Clopper-Pearson method based on the number of observed responses out of 40 subjects

Number of observed responses	8	9	12	16	20
Observed Response Rate	8/40 (20.0%)	9/40 (22.5%)	12/40 (30.0%)	16/40 (40.0%)	20/40 (50.0%)
95% exact CI (%)	(9.1, 35.6)	(10.8, 38.5)	(16.6, 46.5)	(24.9, 56.7)	(33.8, 66.2)

Table 5-6: Two-sided 95% Exact CI Using Clopper-Pearson Method Based on the Number of Observed Responses out of 50 Subjects

Number of observed responses	20	22	26	30	33	35
Observed Response Rate	20/50 (40.0%)	22/50 (44%)	26/50 (52%)	30/50 (60%)	33/50 (66%)	35/50 (70%)
95% exact CI (%)	(26.4, 54.8)	(30.0, 58.8)	(37.4, 66.3)	(45.2, 73.6)	(51.2, 78.8)	(55.4, 82.1)

Table 5-7: Two-sided 95% Exact CI Using Clopper-Pearson Method Based on the Number of Observed Responses out of 35 Subjects

Number of observed responses	3	5	8	10	12	14
Observed Response Rate	3/35 (8.6%)	5/35 (14.3%)	8/35 (22.9%)	10/35 (28.6%)	12/35 (34.3%)	14/35 (40%)

Table 5-7: Two-sided 95% Exact CI Using Clopper-Pearson Method Based on the Number of Observed Responses out of 35 Subjects

Number of observed responses	3	5	8	10	12	14
95% exact CI (%)	(1.8,23.1)	(4.8, 30.3)	(10.4, 40.1)	(14.6, 46.3)	(19.1, 52.2)	(23.9,57.9)

6 STUDY PERIODS, TREATMENT REGIMENS AND POPULATIONS FOR ANALYSES

6.1 Study Periods

6.1.1 Baseline Period

Baseline evaluations or events are defined as evaluations or events that occur before the date and time of the first dose of study treatment.

In cases where the time (onset time of event or evaluation time and dosing time) is missing or not collected, the following definitions will apply:

- Pre-treatment AEs are defined as AEs with an onset date prior to but not including the day of the first dose of study treatment
- Baseline evaluations (laboratory tests, pulse oximetry and vital signs) are defined as evaluations with a date on or prior to the day of first dose of study treatment

If there are multiple valid assessments, the assessment that is closest to a day (and time if collected) of the first dose of study treatment will be used as the baseline in the analyses. If multiple assessments are collected at the same date (and time if collected), the assessment with the latest database entry date (and time if collected) will be considered as baseline.

6.1.2 Post Baseline Period

On-treatment AEs are defined as AEs with an onset date and time on or after the date and time of the first dose of study treatment (or with an onset date on or after the day of first dose of study treatment if time is not collected or is missing). An AE will be counted as on-treatment if the event occurred within 30 (or 100) days of the last dose of study treatment. Specifically, re-initiation study treatment is excluded for the purpose of determining the last dose of study treatment as part of the definition of on-treatment; separate safety analyses for re-initiation therapy may be performed.

On-treatment evaluations (laboratory tests, pulse oximetry, and vital signs) are defined as evaluations taken after the day (and time, if collected and not missing) of first dose of study treatment. An evaluation will be counted as on-treatment if it occurred within 30 (or 100) days of the last dose of study treatment.

Late emergent drug-related AEs are defined as drug-related AEs with an onset date greater than 100 days after the last dose of study treatment in subjects off study treatment.

Table 6.1-1: Primary On-Treatment Definition For Safety in Treated Subjects

Cohort	Option for Re-Initiation	On-Treatment Definition
Neoadjuvant	Yes	On or after first dose of nivolumab and within 30 (or 100) days after last dose of nivolumab prior to re-initiation dosing
Metastatic	No	On or after first dose of study treatment and within 30 (or 100) days after the last dose of study treatment

6.2 Treatment Regimens

Neoadjuvant Cohort:

- Nivolumab administered intravenously (IV) over 30 minutes at 240 mg for 2 doses, on Day 1 and Day 15 (before surgery).

Metastatic Monotherapy Cohort:

- Nivolumab administered IV over 30 minutes at 240 mg every 2 weeks for a maximum of 24 months or until disease progression, unacceptable toxicity, or withdrawal of consent, whichever comes first.

Metastatic Combination Cohort (Combinations A, B, C, and D):

- Combo Arm A: Nivolumab 3 mg/kg IV over 30 minutes every 2 weeks plus Ipilimumab 1 mg/kg IV over 30 minutes every 6 weeks for a maximum of 24 months or until disease progression, unacceptable toxicity, or withdrawal of consent, whichever comes first.
- Combo Arm B: Nivolumab 1 mg/kg IV over 30 minutes plus Ipilimumab 3 mg/kg IV over 30 minutes every 3 weeks for 4 doses followed by Nivolumab 240 mg IV over 30 minutes every 2 weeks for a maximum of 24 months or until disease progression, unacceptable toxicity, or withdrawal of consent, whichever comes first.
- Combo Arm C: Nivolumab 480 mg IV over 30 minutes plus BMS-986016 160 mg IV over 60 minutes administered every 4 weeks for a maximum of 24 month, or until disease progression, unacceptable toxicity, or withdrawal of consent, whichever comes first. Subjects enrolled in Combo C prior to Revised Protocol 05 and on treatment with BMS-986016 80 mg + Nivolumab 240 mg q2W will remain on this dose regimen for the duration of their time on treatment.
- Combo Arm D: Daratumumab 16 mg/kg IV administered weekly for the first 8 weeks. Starting at Week 3, nivolumab 240 mg IV over 30 minutes will be administered every 2 weeks. Nivolumab will be administered before the daratumumab infusion on study days when both study drugs are administered on the same day. Daratumumab 16mg/kg will be administered every 2 weeks from Weeks 9-24. Starting at Week 25, nivolumab 480 mg IV flat dose over 30 minutes every 4 weeks; daratumumab 16 mg/kg every 4 weeks for a

maximum of 24 months or until progression, unacceptable toxicity, or withdrawal of consent, whichever comes first. The infusion rates for the first, second, and subsequent daratumumab infusions should closely follow the specifications of the currently approved (USPI)/pharmacy reference manual.¹⁸³

6.3 Populations for Analyses

6.3.1 Study Cohorts

The tumor types for the neoadjuvant cohort are:

- (N-1): HPV positive SCCHN
- (N-2): HPV negative SCCHN
- (N-3): GYN (Cervical, Vaginal, Vulvar) Carcinoma
- (N-4): Merkel Cell Carcinoma

The diseases or tumor types for the recurrent/metastatic monotherapy cohort are

- (M-1): EBV positive related Gastric cancer,
- (M-2): HPV positive SCCHN
- (M-3): GYN (Cervical, Vaginal, Vulvar) Carcinoma
- (M-4): Merkel Cell carcinoma
- (M-5): Nasopharyngeal Carcinoma (NPC)

The diseases or tumor types for the recurrent/metastatic combination therapy cohort are

- (MC-1a): HPV positive Squamous Cell cancer of the Head and Neck (SCCHN) PD-1/PD-L1 naive: combo A
- (MC-2a): Cervical Carcinoma: combo A
- (MC-2b): Cervical Carcinoma: combo B
- (MC-exp): Squamous Cell Cancer of the Cervix: combo B expansion
- (MC-3a): Anogenital HPV associated tumors (vaginal/vulvar/anal canal/penile) Carcinoma: combo A
- (MC-3b): Anogenital HPV associated tumors (vaginal/vulvar/anal canal/penile) Carcinoma: combo B
- (MC-4a): Merkel Cell Carcinoma: combo A
- (MC-5a): Nasopharyngeal carcinoma (NPC): combo A
- (MC-6c): HPV positive Squamous Cell cancer of the Head and Neck (SCCHN) Prior PD-1/PD-L1: combo C
- (MC-7d): Squamous Cell cancer of the Head and Neck (SCCHN) I-O naive: combo D

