7 STATISTICAL ANALYSES

7.1 General Methods

Unless otherwise noted, the following subsections describe tabulations of discrete variables, by the frequency and proportion of subjects falling into each category. Percentages given in these tables will be rounded and, therefore, may not always sum to 100%. Continuous variables will be summarized using the mean, standard deviation, median, minimum and maximum values. If a missing category is not being presented in the data display, only those subjects with non-missing values for the parameter being assessed are included in the percentage calculation.

Time to event distribution (e.g. progression free survival, overall survival, time to response, and duration of response) will be estimated using Kaplan Meier techniques. When appropriate, the median along with the corresponding log-log transformed 95% CI will be estimated. Rates at fixed time points will be derived from the Kaplan Meier estimate and corresponding confidence intervals will be derived based on Greenwood formula³ for variance derivation and on log-log transformation applied on the survivor function $S(t)$ ⁴.

Confidence intervals for binomial proportions will be derived using the Clopper-Pearson method⁵.

All analyses will be performed separately for each tumor type upon completion of follow-up for the primary endpoint in each tumor type. Safety analyses will also be performed for each tumor type.

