7.5.1.2 Metastatic Cohorts: Objective Response Rate

The ORR based on investigator assessment (Per RECIST 1.1) will be summarized. The Clopper-Pearson method will be used to estimate the two-sided 95% confidence intervals.

BOR will be summarized by response category.

To assess consistency of ORR, investigator-assessed ORR (primary analysis) will be summarized for the following subgroups by tumor type:

- Age (descriptive statistics); Age categories (< 65, ≥ 65 and < 75, ≥ 75)
- Gender (Male, Female)
- Race (White, Black, Asian, and Other)
- Region (US/Canada, Europe, Rest of the World)
- ECOG PS (0/1)
- Time from initial disease diagnosis to study entry (<= 1 year, > 1 year)
- Prior therapy (surgery, radiotherapy, and systemic cancer therapy)
- Prior lines of therapy (1, 2, 3, >=4)

- Number of prior therapy in metastatic settings (0, >=1)
- Prior platinum (yes, no) for SCCHN, GYN, cervical, anogenital HPV associated tumors
- Prior bevacizumab (yes, no) for SCCHN, GYN, cervical, anogenital HPV associated tumors
- Time from completion of most recent prior regimen to study entry (<= 3, <3 - <=6, <6 - <=9, <9 - <=12, >12 months)
- All lesions (Investigator tumor assessments at Baseline): sites of diseases, number of disease sites per subject
- Target Lesions (Investigator tumor assessments at Baseline): presence of target lesions, site of target lesion, sum of diameters of target lesions.
- Virus status (Positive / Negative) in tumor types **(M-3)** GYN (cervical, vaginal, and vulva) Carcinoma, **(MC-2a, MC-2b, MC-exp)** Cervical Carcinoma, **(MC-3a, MC-3b)** Anogenital HPV associated tumors (vaginal/vulvar/anal canal/penile), **(M-4, MC-4a)** Merkel Cell Carcinoma and **(M-5,MC-5a)** Nasopharyngeal Carcinoma (NPC), for which the virus status are tested retrospectively.

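### The cervical Combo B expansion is sized by line of therapy, but the SAP does not say whether it is pooled with the original Combo B cohort and gives ORR by line only as a generic subgroup

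*SAP*

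**What the plan says.** **Sizing.** SAP section 5, matching Protocol 8.1, adds "approximately 50 subjects as first-line treatment for their recurrent/metastatic disease" and "approximately 20 subjects as second-line" to the cervical Combo B cohort, to confirm an efficacy signal. With the original Combo B subjects included, "there should be a total of approximately 75 subjects with first-line treatment and approximately 35 subjects with second-line treatment of cervical cancer". Table 5-4 shows one cervical Combo B cell of 110, footnoted as 40 plus 70.

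**Precision.** Table 5-6 covers n=50; the text says 22 responders exclude 30% and 26 exclude 37%. Table 5-7 covers n=35; the text says 8 responders exclude 10%. Neither table is labelled by line, and there is no table for 75 or 20.

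**Analysis units.** SAP 2.1 and 6.3.1 list MC-2b (cervical, Combo B) and the expansion ("MC-exp): Squamous Cell Cancer of the Cervix: combo B expansion") as separate entries without a line split. SAP 6.3.2 defines populations within each tumor type in each cohort. SAP 7.1 says "All analyses will be performed separately for each tumor type upon completion of follow-up for the primary endpoint in each tumor type", and SAP 7.5 reports efficacy separately by tumor type in different cohorts. Protocol 8.2 and 8.4 work by cohort, tumor type and regimen.

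**Line of therapy.** SAP 7.5.1.2 lists subgroups for checking the consistency of ORR, among them "Number of prior therapy in metastatic settings (0, >=1"). SAP 7.5.2.1, 7.5.2.3 and 7.5.2.4 (DOR, OS, PFS) mention no line split.

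**The concern.** The expansion recruits two groups in fixed numbers, and its two precision tables discuss different response rates (30% and 37% at n=50; 10% at n=35). A reader would expect a named ORR estimate for each group. Taken at face value, SAP 6.3.1 and 7.5 instead yield one ORR for MC-2b (about 40 subjects) and one for MC-exp (about 70), each mixing the lines.

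Two things are at stake. First, the headline MC-exp rate depends on the mix of lines and need not describe either group. Second, if pooling is left open, the by-line sets can be chosen after the data are seen, and the number of responders needed to rule out a given rate depends on that choice. Pooling also carries a cost of its own: MC-2b is an earlier cohort of the same regimen, and the expansion was added to confirm the signal already seen. The expansion alone is therefore the independent confirmation, while the pooled set is the more precise estimate.

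**Working it through.** **Inputs.** Expansion: 50 first-line, 20 second-line. Pooled: 75 and 35 (SAP section 5). By subtraction the original Combo B cohort holds 75 − 50 = 25 first-line and 35 − 20 = 15 second-line, total 40, as in Table 5-4. Interval method, SAP 7.1: "Confidence intervals for binomial proportions will be derived using the Clopper-Pearson method"; the tables are two-sided 95%.

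**Formula.** For x responders of n, the exact lower limit is the 2.5% quantile of Beta(x, n − x + 1). It lies above a rate p0 exactly when P(X ≥ x | n, p0) < 0.025.

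**Reproducing the plan's figures.**
- 8/35: (10.42, 40.14). Agrees with Table 5-7; 10% is excluded.
- 26/50: (37.42, 66.34). Agrees with Table 5-6; 37% is excluded.
- 22/50: (29.99, 58.75). Table 5-6 prints (30.0, 58.8). P(X ≥ 22 | 50, 0.30) = 0.02509, just over 0.025, so 30% is not strictly excluded. The first count that does exclude it is 23/50, with lower limit 31.81%.

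The other entries of Tables 5-6 and 5-7 agree with the recalculation.

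**Which analysis set has which n.**

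| Set | n | Where it appears |
|---|---|---|
| MC-2b, mixed lines | 40 | SAP 6.3.1 |
| MC-exp, mixed lines | 70 | SAP 6.3.1 |
| All cervical Combo B | 110 | Table 5-4; Protocol 8.4 reading |
| MC-exp, 0 prior | 50 | SAP 7.5.1.2 subgroup, cohorts separate; Table 5-6 |
| MC-exp, at least 1 prior | 20 | SAP 7.5.1.2 subgroup, cohorts separate; no table |
| Pooled, 0 prior | 75 | SAP 7.5.1.2 subgroup only if pooled; no table |
| Pooled, at least 1 prior | 35 | SAP 7.5.1.2 subgroup only if pooled; Table 5-7 |

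The two tables therefore fit different pooling rules: n=50 fits the expansion alone and n=35 fits the pooled set.

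**Smallest count whose lower limit exceeds the rate.**

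| Rate excluded | Set | Count | Observed ORR | Lower limit |
|---|---|---|---|---|
| 10% | pooled second-line, n=35 | 8 | 22.9% | 10.42% |
| 10% | expansion second-line, n=20 | 6 | 30.0% | 11.89% |
| 30% | pooled first-line, n=75 | 31 | 41.3% | 30.08% |
| 30% | expansion first-line, n=50 | 23 | 46.0% | 31.81% |
| 30% | MC-exp mixed, n=70 | 30 | 42.9% | 31.09% |
| 30% | all cervical Combo B, n=110 | 44 | 40.0% | 30.78% |

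**How much pooling matters for second line.** The chance of reaching the count is P(X ≥ 8 | 35, p) pooled and P(X ≥ 6 | 20, p) in the expansion alone. With an assumed true ORR of 25% these are 68% and 38%; with 30% they are 87% and 58%. At an observed ORR near 23% to 25%, the half-width of the interval is about 15 points at n=35 (8/35) and 20 points at n=20 (5/20).

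**Mixing.** With assumed true rates of 40% first-line and 20% second-line, the MC-exp rate is (0.40 × 50 + 0.20 × 20)/70 = 24/70 = 34.3%. This is an illustration only; the documents give no expected rate by line.

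**The case against.** A reader might infer that the stated precision applies to no planned analysis. That goes too far. The subgroup with no prior metastatic therapy within MC-exp is planned and holds about 50 subjects, which is the n of Table 5-6.

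A reader might also infer that the two cohorts are definitely analysed apart, so that a second-line set of 35 never arises. The documents do not settle this. Protocol 8.2 and 8.4 use cohort, tumor type and regimen; Table 5-4 has one cell of 110; the subgroup list in SAP 7.5.1.2 is by tumor type; and SAP 7.9.2 puts MC-2a, MC-2b and MC-exp under one cervical label. On that reading the subgroup with at least one prior therapy has about 35 subjects and Table 5-7 fits. Separate analysis is the more natural reading of SAP 6.3.1 and 7.5, but not the only one.

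Nor is 8/35, or 22/50, a success criterion. Both documents say that sample size does not rest on a power calculation, and the tables describe where a confidence limit falls. The documents never assign 30% and 37% to first line; that link is inferred from n. Finally, the protocol's primary objective is ORR in metastatic or recurrent cervical cancer without a line split, so by-line ORR should not replace it.

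These objections stand and narrow the point. They do not remove it: the analysis set is unsettled, and a generic consistency subgroup is a thin home for the estimates that the expansion was sized to give. The category of at least one prior therapy is also not strictly second-line, since Protocol 3.3.1 allows up to two prior regimens, and the other subgroup (1, 2, 3, at least 4 lines) has no zero category.

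**Conclusion.** The concern holds as a gap between how the expansion is sized and how it is analysed. The plan counts subjects by line, partly pooled, but leaves the pooling of MC-2b and MC-exp open, names no by-line analysis set, gives no precision for 75 or 20, and has no line split for DOR, PFS or OS.

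The choice it leaves open is material. Excluding 10% in second line takes an observed 22.9% if pooled and 30% in the expansion alone. Excluding 30% in first line takes 41.3% pooled and 46% in the expansion alone. Separately, the statement that 22/50 excludes 30% is wrong by a hair and should read 23/50.

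These figures assume that the planned counts are met exactly, that Tables 5-6 and 5-7 refer to first and second line as their n suggests, and that the 25 and 15 in the original cohort follow by subtraction. The plan is not invalid, and its primary ORR can be reported as it stands. The change is a cheap improvement that should be made.

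**What to change.** In SAP 6.3.1, define first-line and second-line sets for cervical Combo B, with a rule for subjects who had two prior regimens, and state whether MC-2b and MC-exp are pooled for the primary ORR.

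In SAP 7.5.1.2, pre-specify ORR with an exact 95% interval by line, for MC-exp alone and for MC-2b plus MC-exp. Present it alongside the protocol's primary ORR, not in its place. Apply the same split to DOR, PFS and OS in SAP 7.5.2.

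In SAP section 5, say which set Tables 5-6 and 5-7 describe, add precision for n=75 and n=20, and change 22/50 to 23/50 (46%) for excluding 30%. Protocol 8.1 carries the same sentence and table.

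**Cost.** A few more tables. By-line intervals are wider than the mixed-cohort interval: the half-width near 23% to 25% ORR is about 20 points at n=20 (5/20), against about 10 points at n=70 (16/70). No new data appear to be needed, because SAP 7.3.4 already summarises prior metastatic therapies as 0, 1 or 2.
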